11/20/2023

[figure not shown]
Dear FDA Clinical Trials Review Board,

Please find attached the *study protocol and statistical analysis plan* document as requested on the PRS System.

This is for the study: *Intracanalicular Dexamethasone Insert for Post-Corneal Cross-Linking Inflammation and Pain- The LINK Study* (IND 146603; NCT04168112)

Please do not hesitate to contact me with any questions or concerns regarding this document.
Thank you for your time and consideration.

Sincerely,

[name], DO
SightMD
[name]
[name]
[contact]

*Intracanalicular Dexamethasone Insert for Post-Corneal Cross-Linking Inflammation and Pain-
The LINK Study*

Protocol in brief: This prospective, open-label, single-center, randomized, investigator-sponsored clinical study sought to investigate the efficacy of dexamethasone intracanalicular insert on post-corneal crosslinking inflammation and pain in keratoconus patients. This study planned to enroll 20 patients and follow patients over the course of several study visits [(postoperative day (POD) 1, POD-3, POD4-7, POW2, POW3 and POW4]. It is anticipated that corneal re-epithelialization will occur within the first postoperative week, but patients were be followed closely for documentation of therapeutic effect for 30 days due to duration of steroid therapy (i.e. dexamethasone intracanalicular insert or use of Prednisolone acetate 1% ophthalmic solution tapered over 1 month in the following schedule: 4 times daily x1 week, 3 times daily x 1 week, 2 times daily x 1 week, and daily x 1 week). All patients will receive postoperative fluoroquinolone antibiotic eye drops with instructions for use (i.e. 1 drop in operative eye 4 times daily x 10 days). All patients were evaluated for pain scores, rate of corneal re-epithelialization, ease of use of the post-crosslinking regimen, and need for rescue pain medication after standard bilateral epithelium-off crosslinking.

Biostatistics

Study variables were analyzed by appropriate statistical methods to assess for the differences between eyes treated as an entire group, and as broken down between dexamethasone implant and traditional prednisolone drop groups. Correlations between ease of use, intraocular inflammation, and epithelial healing were assessed using χ^2 , t-test, Pearson, and the Fisher Z-transformation test, evaluating the sample correlation r for significance. For independent samples, the t-test or Mann-Whitney-U test will be used for scaled data based on the outcome of the Kolmogorov-Smirnov test for normality of distribution. Ordinal data was analyzed using the Mann-Whitney-U test and chi-square or Fisher's Exact test for nominal data. P-values less than or equal to 0.05 were considered statistically significant. For non-inferiority or equivalency data, 95% confidence intervals were formulated and compared with equivalency margins. Sample size is small secondary to the incidence of the disease (1:2,000)

For any patient deciding to withdraw from the follow-up, the reasons for the withdrawal were recorded for the subsequent analysis in the interpretation of the results. Reasons behind drop out were investigated and included in study results. The authors only analyzed complete cases, as imputing the missing data using single or multiple imputation methods would be confounded by the small sample size. ITT for ease of use was calculated utilizing extremely conservative estimates of a 70% +/- 10% for drops and 90% for dexamethasone insert, while utilizing a two independent sample study with a continuous endpoint, 1:1 enrollment ratio, alpha/beta of 0.05, and power of 95%. We calculated the minimum number of patients needed to enroll as 12.

In order to account for type I errors over multiple endpoints Bonferroni adjustment method was utilized.

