When assessing pain scores, a standardized visual analog pain scale (0-10) was used for each patient. Mean pain score on POD0 was 6.4 ± 1.3 and 6.6 ± 1.62 for the prednisolone and dexamethasone insert groups, respectively. Pain scores fell significantly on POD1 to 1.3 ± 0.45 and 2 ± 1.18 in the prednisolone and dexamethasone groups, respectively. By POD7, no patient complained of pain or discomfort (i.e., pain scale rating was “0”). No patient used ‘rescue medications’ longer than 2 days (POD0 and POD1) – the most commonly used self-reported medications were ibuprofen and acetaminophen. Seventy percent of patients in the prednisolone group vs. 60% of those patients in the dexamethasone insert group self-administered pain medications to help manage postoperative discomfort. No narcotics were prescribed or deemed necessary to help manage post-CXL pain in our study. Though not a large difference in pain scores, those in the prednisolone group reported statistically significantly lower pain scores at POD0 (t-test, $p=0.021$) and POD1 (t-test, $p=0.036$) vs. those in the dexamethasone insert group.

Ocular surface inflammation was noted to be quite mild over the course of the study. Most patients demonstrated clear conjunctiva that was free of injection by POD1; only 4 eyes (2 in the prednisolone group, 2 in dexamethasone group) had trace injection noted at time of exam. No conjunctival injection was noted at the remainder of the study visits for any subject.

Trend in intraocular pressure (IOP) was assessed from baseline to POW4. There was no significant difference in baseline IOP between groups (t-test, $p=0.518$); mean IOP was noted to be 13.5 ± 1.28 mmHg and 13.9 ± 1.64 mmHg at POD1 in prednisolone and dexamethasone insert groups, respectively. By POW4, mean IOP measured 14.25 ± 1.64 mmHg in the prednisolone

group and 13.65 ± 2.26 mmHg in the dexamethasone insert group. There was no significant rise or difference in intraocular pressure over time across both groups.

Rate of corneal re-epithelialization was assessed between groups. There was no significant difference between groups and rate of epithelial defect resolution at POD1 (t-test, $p=0.152$) and POD3 ($p=0.061$). Epithelial defect was noted to be resolved by POD7 in all subjects

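### The available text names no primary outcome or time point, so the reported pain difference favouring prednisolone has no confirmatory standing and depends on an undefined Bonferroni family

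*Combined protocol and SAP*

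**What the plan says.** The Protocol in brief states that the study "sought to investigate the efficacy of dexamethasone intracanalicular insert on post-corneal crosslinking inflammation and pain in keratoconus patients". It then lists what was measured, with no ranking and no deciding time point: "All patients were evaluated for pain scores, rate of corneal re-epithelialization, ease of use of the post-crosslinking regimen, and need for rescue pain medication". Inflammation, half of the stated aim, is not in that list. On size it says: "This study planned to enroll 20 patients".

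The Biostatistics section has one power statement, and it concerns ease of use: "ITT for ease of use was calculated utilizing extremely conservative estimates of a 70% +/- 10% for drops and 90% for dexamethasone insert". The design is given as a "two independent sample study with a continuous endpoint, 1:1 enrollment ratio, alpha/beta of 0.05, and power of 95" percent, and the section concludes: "We calculated the minimum number of patients needed to enroll as 12". The significance rule is "P-values less than or equal to 0.05 were considered statistically significant". The section also says that Bonferroni was used across multiple endpoints, but gives no family, number of tests or adjusted threshold.

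The results narrative reports that "those in the prednisolone group reported statistically significantly lower pain scores at POD0" (p = 0.021), and says the same for POD1 (p = 0.036).

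**The concern.** A confirmatory claim needs a comparison that was fixed before the data were seen. Here the aim, the power statement and the outcome list each point to a different comparison, and none is called primary. A reader cannot tell which result answers the trial's question.

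This matters because the one between-arm difference reported as significant runs against the insert and sits on an endpoint with no planned effect size. The other outcomes show no demonstrated difference. Whether the trial is summarised as showing less pain with prednisolone or as showing no established difference depends on a choice of endpoint and a count of tests that the text does not give. Bonferroni limits error across a set of tests, but it does not say which test is the trial's question, and without a stated family it cannot be applied.

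**Working it through.** **1. What the power statement covers.** Inputs from Biostatistics: difference 90 − 70 = 20, SD taken as 10 in both arms, alpha 0.05, power 95%, 1:1. Per arm, n = 2 × ((z_alpha + z_beta) × SD / difference)².
- One-sided: 2 × ((1.645 + 1.645) × 10/20)² = 5.4, so 6 per arm and 12 in total. This matches the stated 12.
- Two-sided: 2 × ((1.960 + 1.645) × 10/20)² = 6.5, so 7 per arm and 14 in total.
- If 70% and 90% were proportions answering yes, n = [1.960 × √(2 × 0.8 × 0.2) + 1.645 × √(0.21 + 0.09)]² / 0.2² = 101 per arm (two-sided), far from 12.

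So the 95% power belongs to a continuous ease-of-use score. The results report yes/no items, and the second of these pertained to the prednisolone group, so it offers no between-arm contrast. No effect size is planned for pain. With 10 per arm (assumed from 20 patients, 1:1), a single pain comparison has 80% power only for a difference of 1.32 SD at alpha 0.05, or 1.64 SD at 0.0125.

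**2. The pain p-values under Bonferroni, if they are unadjusted.** Threshold = 0.05/k.

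| k | threshold | POD0, 0.021 | POD1, 0.036 |
|---|---|---|---|
| 2 | 0.025 | passes | fails |
| 3 | 0.0167 | fails | fails |
| 4 | 0.0125 | fails | fails |
| 6 | 0.0083 | fails | fails |

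The Protocol in brief lists four outcomes. The results also print four post-treatment between-arm p-values (pain at POD0 and POD1; healing at POD1 and POD3, 0.152 and 0.061). Either count gives 0.0125.

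**3. Family-wise error if Bonferroni was not applied.** With independent tests at 0.05 and no true effect, 1 − 0.95⁴ = 0.185 and 1 − 0.95⁶ = 0.265. Simulation with equicorrelated normal statistics (1,000,000 draws) gives, at correlation 0.5 and 0.8:
- four tests: 0.156 and 0.114;
- six tests: 0.208 and 0.138.

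The six are pain at POD0 and POD1, healing at POD1 and POD3, and IOP and CCT at POW4. The correlations are assumptions.

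**4. Do the printed summaries give the printed pain p-values?** Two-sample t-test, t = difference / √((SD1² + SD2²)/n).
- POD0, 6.4 (1.3) vs 6.6 (1.62): n = 10 gives 0.2/√(4.3144/10) = 0.2/0.657, t = 0.30, p = 0.76. n = 20 eyes gives 0.2/0.464, t = 0.43, p = 0.67. About 577 per arm would be needed to reach the stated 0.021.
- POD1, 1.3 (0.45) vs 2 (1.18): n = 10 gives 0.7/0.399, t = 1.75, p = 0.097. n = 20 eyes gives 0.7/0.282, t = 2.48, p = 0.018. The stated 0.036 lies between these.

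Both values of n are assumptions from 20 patients, 1:1 and bilateral treatment. The 20-eye version also treats fellow eyes as independent.

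**5. The other outcomes.** Trace injection was 2 vs 2 eyes. Healing was not significantly different. Rescue use was 70% with prednisolone and 60% with the insert; at an assumed 7/10 vs 6/10, Fisher's exact p = 1.0.

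**The case against.** Several points on the other side are sound.

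- **The text is incomplete.** A part between Biostatistics and the pain results was not available, and the study has a registry record that was not consulted. This stands: the finding is that no primary is named in the available text, not that none was ever set.
- **Bonferroni is stated.** If it was applied over all the tests, family-wise error is at most 5%. A reader might infer that the trial ran at a 21% error rate. The text does not support that as a flat statement, so the rates in step 3 are conditional. If the printed p-values are already adjusted, they may be read against 0.05 and the failures in step 2 disappear. A primary would still be missing, and the POD0 discrepancy would widen: 0.021 adjusted over four tests implies an unadjusted value near 0.021/4 = 0.005.
- **The outcomes do not truly conflict.** A reader might infer that they give opposing answers. They do not: one is reported as significant, the rest are null or uniform, and the rescue difference amounts to nothing at these numbers.
- **The report is restrained.** It concedes that the pain difference is not large and never calls pain primary. That is fair, but it still makes a significance claim.
- **Ease of use looks like the implied primary.** A reader might infer that, being the only powered endpoint, it is the confirmatory one and was negative. Sizing on an endpoint does not make it primary, it is absent from the stated aim, and what was collected does not match the continuous score that was sized. Naming it now would choose a primary after the data.

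**Conclusion.** The concern holds in a limited form. The available text fixes no primary outcome or time point, and its only power statement does not apply to pain or inflammation. The pain claim therefore has no confirmatory standing. Whether it survives the plan's own multiplicity rule depends on two unstated facts: the Bonferroni family, and whether the printed values are adjusted. If they are unadjusted, POD1 fails with two or more tests and POD0 with three or more.

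The POD0 p-value does not follow from its printed means and SDs under either assumed count, and that problem does not depend on multiplicity. The documents do not establish that the type I error was in fact inflated, that the endpoints contradict each other, or that ease of use was the primary.

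**What to change.** - Search for a pre-data record naming a primary outcome and time point. If there is one, cite it and report that contrast as the confirmatory one. If not, state that the trial has no confirmatory endpoint and label every between-arm comparison exploratory, each with an estimate and 95% CI. Do not declare ease of use, or any other outcome, primary now.
- Replace the significance claim for pain with an exploratory statement. From the printed summaries at an assumed 10 per arm (t quantile 2.101, 18 df), insert minus prednisolone is 0.2 ± 2.101 × 0.657, or −1.18 to 1.58, at POD0, and 0.7 ± 2.101 × 0.399, or −0.14 to 1.54, at POD1. These should be recomputed from the data.
- State the Bonferroni family, the adjusted threshold, and whether the printed p-values are adjusted.
- Recheck the POD0 p-value against the source data, and state whether patients or eyes were analysed.
- State that the 95% power refers only to a continuous ease-of-use score. Report the yes/no answers descriptively, not as evidence of equivalence, and note that the second question pertained only to the prednisolone group.

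The cost is rewording and a short reanalysis, with no new patients or data. The downside is that the pain result loses its significance claim.

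### After bilateral crosslinking the plan compares eyes with independent-sample tests and gives no method for fellow-eye correlation, so precision for IOP, CCT and epithelial defect may be overstated.

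*Combined protocol and SAP*

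**What the plan says.** The Protocol in brief plans 20 patients and lists among the outcomes "need for rescue pain medication after standard bilateral epithelium-off crosslinking". So each patient contributes two treated eyes.

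The Biostatistics section sets the comparison as one to "assess for the differences between eyes treated as an entire group, and as broken down between dexamethasone implant and traditional prednisolone drop groups". For the test it says: "For independent samples, the t-test or Mann-Whitney-U test will be used for scaled data". Ordinal data go to Mann-Whitney and nominal data to chi-square or Fisher's exact. Pearson correlation and the Fisher Z-transformation are listed for correlations. None of these allows for two correlated eyes from one person.

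The same section counts the design in patients. The sample size is described as "utilizing a two independent sample study with a continuous endpoint, 1:1 enrollment ratio", and it concludes: "We calculated the minimum number of patients needed to enroll as 12". It also says: "For non-inferiority or equivalency data, 95% confidence intervals were formulated and compared with equivalency margins". No outcome or margin is named there.

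The results text mixes units. Rescue medication is given by patient: "Seventy percent of patients in the prednisolone group vs. 60% of those patients in the dexamethasone insert group". Conjunctival injection is given by eye: "only 4 eyes (2 in the prednisolone group, 2 in dexamethasone group) had trace injection noted at time of exam". IOP, CCT and epithelial defect are compared between groups with no n. A stretch of text between the Biostatistics section and the pain results was not available for this review.

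**The concern.** Two eyes of one patient usually resemble each other in IOP, corneal thickness and healing. If both are in the same arm and each is entered as a separate observation in an independent-sample test, the standard error is too small and the degrees of freedom too many.

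The safety and healing message of this trial rests on the absence of significant differences in IOP, CCT and epithelial defect. Such a finding is only as informative as its interval. Intervals that are too narrow also favour any equivalence or non-inferiority claim, which the plan provides for. The direction depends on allocation: if fellow eyes had been split between arms, the same tests would be conservative instead.

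**Working it through.** **The plan's own figure.** With 70 versus 90 for ease of use, SD read as 10, α 0.05 and power 95%, n per arm = 2(z_α + z_β)²(SD/δ)².
- One-sided: 2 × (1.645 + 1.645)² × (10/20)² = 5.41, so 6 per arm and 12 in total, as stated.
- Two-sided: 2 × (1.960 + 1.645)² × 0.25 = 6.50, so 7 per arm and 14 in total.

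This is a patient-level figure with no inter-eye term. It is not affected by the concern, but it shows that the design was counted in patients.

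**Do both eyes share an arm?** Rescue use of 70% and 60% of patients in each group fits 7/10 and 6/10 of the 20 planned. A percentage of patients per group would make little sense if each patient had one eye in each arm.

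**Were eyes the unit?** This is not stated, but the printed summaries give a hint if IOP was recorded in whole mmHg.
- POW4 means of 14.25 and 13.65 cannot come from 10 single readings (sums 142.5 and 136.5). They can come from 20 (sums 285 and 273).
- All four printed IOP mean/SD pairs (POD1 and POW4) fit 20 whole-number values with a divisor-n SD.
- Averages of two eyes in 10 patients do not fit all four under one SD definition. Divisor n−1 fails both POD1 pairs, and divisor n fails 14.25 ± 1.64.

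**Size of the effect.** Assumptions: 10 patients and 20 eyes per arm, both eyes in the same arm, inter-eye correlation ρ not given and therefore ranged.
- Effective n per arm = 20/(1 + ρ).
- Interval ratio = √(1 + ρ) × t(0.975; 18)/t(0.975; 38) = √(1 + ρ) × 2.101/2.024.
- Type I error comes from 100,000 simulated null trials per ρ, using an eye-level t-test at nominal 5%. Repeat runs agreed to about 0.3 percentage points.

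| ρ | Effective n per arm | Interval wider by | True type I error |
|---|---|---|---|
| 0 | 20 | – | 5.0% |
| 0.3 | 15.4 | 18% | 8.8% |
| 0.5 | 13.3 | 27% | 11.3% |
| 0.8 | 11.1 | 39% | 15.2% |
| 0.9 | 10.5 | 43% | 16.5% |

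A t-test on patient means holds 4.9% to 5.1% throughout. With fellow eyes split between arms, the independent t-test rejects in 2.0%, 0.7%, 0.01% and 0.0% of trials at the same four non-zero ρ.

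**Reported p-values, if they came from 20 eyes per arm.** Take t at 38 df, divide by √(1 + ρ), and read at 18 df. For POD3, t = 1.931; at ρ = 0.3, 1.931/1.140 = 1.694, p = 0.108. Only the first two rows are labelled as t-tests in the results; POD3 is assumed to be one.

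| Comparison | Printed p | t, 38 df | p at ρ 0.3 to 0.9 |
|---|---|---|---|
| Baseline IOP | 0.518 | 0.653 | 0.574 to 0.642 |
| Epithelial defect POD1 | 0.152 | 1.462 | 0.216 to 0.303 |
| Epithelial defect POD3 | 0.061 | 1.931 | 0.108 to 0.178 |

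**POW4 intervals, if the printed SDs are eye-level.** Half-width = t × √[(s₁² + s₂²)(1 + ρ)/20], with ρ = 0 and 38 df for the naive case and 18 df otherwise. Differences are dexamethasone minus prednisolone.
- IOP, difference 13.65 − 14.25 = −0.60 mmHg. Naive SE = √[(1.64² + 2.26²)/20] = 0.624, half-width 1.26, interval −1.86 to 0.66 (p = 0.343). At ρ 0.5: −2.21 to 1.01. At ρ 0.9: −2.41 to 1.21 (p = 0.495).
- CCT, difference 473.15 − 459 = 14.15 μm. Naive SE = √[(33.89² + 43.78²)/20] = 12.38, half-width 25.1, interval −10.9 to 39.2 (p = 0.260). At ρ 0.5: −17.7 to 46.0. At ρ 0.9: −21.7 to 50.0 (p = 0.418).

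If the printed SDs use divisor n, the half-widths go from 1.30 to 1.54–1.86 mmHg and from 25.7 to 30.4–36.8 μm over ρ 0.3 to 0.9. If they are already SDs of 10 patient means (divisor n−1), the half-widths are 1.86 mmHg (p = 0.506) and 36.8 μm (p = 0.430), and no correction is due.

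**The case against.** The strongest reply is that the defect is conditional. No available sentence says that fellow eyes were entered as independent observations; naming a test for independent samples does not declare the eyes independent. Some wording points to one value per patient: the Protocol in brief refers to the treated eye in the singular, and the results give defect closure by POD7 for subjects. Eye counts or allocation could be in the text that was not available. This stands as a limit on certainty. It does not supply a method: the section names eyes as what is compared and lists no test that handles pairs.

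Second, the plan uses a Bonferroni adjustment, so 5% may not be the operative level. The number of endpoints is not given. With five assumed, a nominal 1% eye-level test has a true error of about 2.5% to 6.7% over the same correlations. The absolute figure is smaller, but the error is still inflated.

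Third, no eye-level result was declared significant, and no interval, margin or equivalence claim is printed for these outcomes. This is true, and it limits the harm to precision.

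Fourth, the converted p-values look more exact than they are. The printed POD0 pain p-value of 0.021 does not follow from its own summaries (0.76 with 10 per arm, 0.67 with 20), so the printed p-values may not come from simple t-tests on the stated data. The conversions show direction and rough size only. The whole-mmHg check likewise concerns how summaries were computed, not how tests were run.

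**Conclusion.** The concern holds as a gap in the analysis plan with a likely, but not proven, effect on the results. Followed as written, with both eyes in the same arm, the plan yields standard errors that are too small: true intervals are 18% to 43% wider for an assumed inter-eye correlation of 0.3 to 0.9. The findings of no difference for IOP, CCT and epithelial defect then carry less information than the tests imply, as would any equivalence reading.

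No reported eye-level conclusion changes, since correction only raises p-values that are already above 0.05. The size rests on three assumptions: 10 patients per arm, both eyes in one arm, and eyes as the unit. Confidence is medium because the unit is inferred. The point should be fixed, but it does not overturn the trial.

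**What to change.** - State the unit of randomization, and the unit of analysis for each outcome.
- For eye-level outcomes, make the patient the unit: the mean of the two eyes for IOP and CCT, and a per-patient summary for epithelial defect. A mixed model or GEE clustered on patient, with a small-sample correction, is an alternative.
- If fellow eyes were in different arms, use a paired analysis.
- Re-run the reported eye-level tests and any equivalence intervals on the existing data, and print the number of patients and eyes behind each.
- If one value per patient was already used, a sentence saying so is enough.

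The cost is a few lines of SAP text and a re-run; no new data are needed. The downside, if eyes were the unit, is the wider intervals shown above, which are the honest ones.

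### Re-epithelialization, IOP over time and CCT are reported only as non-significant, with no between-arm confidence interval, so the report does not show which differences are excluded

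*Combined protocol and SAP*

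**What the plan says.** The Biostatistics section gives two criteria. For tests of difference: "P-values less than or equal to 0.05 were considered statistically significant". For similarity, where data are of a non-inferiority or equivalence kind: "95% confidence intervals were formulated and compared with equivalency margins". The second is conditional. It does not say which endpoints count as non-inferiority or equivalence data, and no margin is given for any endpoint. The section also says: "In order to account for type I errors over multiple endpoints Bonferroni adjustment method was utilized", without giving the number of tests.

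The results narrative then reports:

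- **Re-epithelialization:** "There was no significant difference between groups and rate of epithelial defect resolution", with p=0.152 at POD1 (t-test) and p=0.061 at POD3 (no test named). Neither arm's estimate is printed. All defects had resolved by POD7.
- **IOP:** "There was no significant rise or difference in intraocular pressure over time across both groups". Means and SDs are given at POD1 and POW4, but no p-value for the comparison over time.
- **CCT:** no significant difference at baseline or POW4. Means and SDs are given, with no p-value.

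No between-arm confidence interval appears for any of these outcomes.

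**The concern.** A p-value above 0.05 does not show that two arms are alike. In a trial this small it is a likely result even when the true difference is substantial. The Biostatistics section describes a method that could address similarity, an interval set against a margin, and says in the past tense that it was carried out. A reader who then meets several statements of non-significance may take them as the output of that method. Nothing printed shows that they are.

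At stake is how the healing and CCT results are read. If the intervals are wide, the accurate description is inconclusive. If an interval is reasonably narrow, as for IOP, the report gives up useful information by leaving it out.

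**Working it through.** **Inputs.** Planned enrolment is 20 patients (Protocol in brief). I assume an even split, 10 per arm, from the 1:1 ratio in the sample-size text. Treatment was bilateral and the unit of each test is not stated, so I show both 10 patients and 20 eyes per arm. The eye-level intervals treat a patient's two eyes as independent and are therefore probably too narrow.

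**The plan's own figure.** The minimum of 12 patients comes from the ease-of-use calculation: 70 against 90, SD 10, "two independent sample study with a continuous endpoint, 1:1 enrollment ratio, alpha/beta of 0.05, and power of 95"%. With n per arm = 2 × [SD × (z_alpha + z_power) / difference]²:

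- one-sided: 2 × [10 × (1.645 + 1.645) / 20]² = 5.41, rounded up to 6 per arm, 12 in total;
- two-sided: 2 × [10 × (1.960 + 1.645) / 20]² = 6.50, rounded up to 7 per arm, 14 in total.

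The 12 reproduces on a one-sided reading. It is a superiority calculation for a 2 SD difference in ease of use, so it gives no basis for concluding similarity in healing, IOP or CCT.

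**Power to detect a difference** (two-sided t-test, 0.05):

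| True difference | 10 per arm | 20 per arm |
|---|---|---|
| 0.8 SD | 40% | 69% |
| 1.0 SD | 56% | 87% |
| 1.2 SD | 72% | 96% |

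**Intervals from reported means and SDs.** Difference = insert minus prednisolone; SE = sqrt[(SD1² + SD2²)/n]; 95% CI = difference ± t × SE, with t = 2.101 (18 df) or 2.024 (38 df).

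*CCT at POW4:* 473.15 - 459 = +14.15 µm.
- 10 per arm: SE = sqrt[(33.89² + 43.78²)/10] = 17.51; half-width 36.8; CI -22.6 to 50.9.
- 20 per arm: SE = 12.38; half-width 25.1; CI -10.9 to 39.2.

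*IOP at POW4:* 13.65 - 14.25 = -0.60 mmHg.
- 10 per arm: SE = sqrt[(1.64² + 2.26²)/10] = 0.883; half-width 1.86; CI -2.46 to 1.26.
- 20 per arm: SE = 0.624; half-width 1.26; CI -1.86 to 0.66.

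**Re-epithelialization, illustrative only.** With no means or SDs, the only route is back from the p-value. If it is an unadjusted two-sided t-test, the standardized difference is d = t_p × sqrt(2/n), with half-width t × sqrt(2/n), which is 0.94 at 10 per arm and 0.64 at 20.

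| | 10 per arm | 20 eyes per arm |
|---|---|---|
| POD3, p=0.061 | t_p = 1.998; 0.89 SD (-0.05 to 1.83) | t_p = 1.931; 0.61 SD (-0.03 to 1.25) |
| POD1, p=0.152 | t_p = 1.496; 0.67 SD (-0.27 to 1.61) | t_p = 1.462; 0.46 SD (-0.18 to 1.10) |

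The sign is arbitrary, because the document does not say which arm healed faster.

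**Can the printed p-values bear this?** Pain scores have both summary data and p-values, so they allow a check. POD0 (6.4 ± 1.3 against 6.6 ± 1.62) gives p=0.76 at 10 per arm or 0.67 at 20, against 0.021 printed. POD1 (1.3 ± 0.45 against 2 ± 1.18) gives 0.097 or 0.018, against 0.036 printed. The POD0 value does not reproduce on either unit, so effect sizes inferred from a bare p-value in this document need caution. The CCT and IOP intervals do not depend on printed p-values.

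**The case against.** The strongest reply is that no planned rule was broken. The margin sentence applies to non-inferiority or equivalence data, no outcome is labelled as such, and the same section plans ordinary tests at 0.05, which is how the results are reported. **This stands.** A reader might infer that a p-value rule was substituted for a planned interval rule; the text does not support that, because it never assigns these outcomes to the interval rule.

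A reader might also infer that the trial's message is that insert and drops perform alike. The document does not say so. It never calls an outcome equivalent or non-inferior, and it reports lower pain scores with prednisolone. **This stands too:** the problem is the risk of misreading, not a false claim.

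Other points on that side:

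- *Part of the text between the statistics and the results was not available for this review.* A margin or interval there cannot be ruled out, so nothing can be said about every statement in the full document. The visible reports of these three outcomes still lack intervals.
- *IOP is fairly well bounded.* Agreed. In the direction of higher pressure with the insert, the upper limit is 1.3 or 0.7 mmHg. It would be wrong to say that large IOP differences remain open.
- *The POD3 effect size is fragile.* Agreed: no test is named, a Mann-Whitney test was allowed, and it is unclear whether Bonferroni applies to this p-value. Nor should 0.061 be called nearly a difference, since a Bonferroni threshold would be stricter than 0.05.
- *All defects had resolved by POD7.* True, and it limits how long any difference could last. It does not settle healing at POD1 and POD3.
- *The baseline comparisons describe balance.* Agreed; they are outside this point.

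**Conclusion.** The concern holds as a reporting fault. For re-epithelialization, IOP over time and CCT, the available text gives non-significance without an interval, next to a margin rule that names neither endpoint nor margin. At 10 per arm, non-significance is weak evidence: a true 0.8 SD difference would be missed about 60% of the time (100% - 40%).

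The strength differs by outcome. CCT is inconclusive, with differences up to about 51 µm (or 39 µm on eyes) not excluded. Healing at POD1 and POD3 cannot be assessed as printed, and the back-calculation only suggests a wide interval. IOP is reasonably bounded. Whether any of these limits matters clinically cannot be judged against the plan, because it gives no margin.

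This rests on an assumed 10/10 split with complete data, t-based intervals and, for healing, an unadjusted two-sided t-test. The unit of analysis is unknown, so both are shown.

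**What to change.** For re-epithelialization at POD1 and POD3, IOP at POW4 and CCT at POW4, report each arm's estimate, the between-arm difference with its direction, and a 95% CI, with the patient as the unit or with a method that allows for two eyes per patient. Name the test behind each p-value and say whether it is Bonferroni-adjusted. State the largest difference that each interval does not exclude, and describe healing and CCT as inconclusive where the interval is wide.

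Either delete the equivalence-margin sentence or limit it to named endpoints whose margin was fixed before the data were seen, quoting the margin. A margin chosen now would not serve. The baseline comparisons need no change.

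The cost is a few lines of reporting from data already in hand; the downside is a more cautious conclusion.
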